Study Title: Effectiveness of KeraStat Gel for Improved Cosmesis of Partial Thickness Burns

NCT03564795

SUMMARY	2
BACKGROUND, RATIONALE AND CONTEXT	2
BACKGROUND.....	2
RATIONALE.....	3
OBJECTIVES	3
METHODS AND MEASURES	4
DESIGN.....	4
SETTING.....	6
SUBJECTS SELECTION CRITERIA.....	6
INTERVENTIONS AND INTERACTIONS.....	7
AGENT DESCRIPTION	7
AGENT ADMINISTRATION.....	8
SCHEDULE OF EVENTS	9
STUDY SUBJECT WITHDRAWAL	14
ANALYTICAL PLAN.....	14
HUMAN SUBJECTS PROTECTION	15

Summary

This study seeks to determine whether the use of KeraStat Gel as the primary dressing for partial thickness burns (1) results in improved healed wound cosmesis and (2) results in less painful dressing changes, faster reepithelialization, and reduction in need for excision and grafting. The study design is a within subject control. Each of two distinct burns will be randomized to the use of KeraStat Gel or standard of care (SOC). The length of study participation for a subject is 1 year. Subjects complete 2 office visits and 2 remote visits during the first month then office visits at months 3, 6, and 12 post burn.

Subjects will complete a visual analog scale for pain during dressing changes, and the reepithelialization of the wound will be noted. During remote visits on days 7 and 21, subjects may complete a digital VAS scale and collect a photo of the wound. At months 3, 6, and 12, subjects and study personnel will complete the Patient Observer Scar Assessment Scale (POSAS). During month 3, 6, and 12 visits, the scars will be subjected to measurement of transepidermal water loss (TEWL) measured with a Tewameter. The wound sites will be photographed at each site visit.

Background, Rationale and Context

Background

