KeraStat® Gel is a sterile, non-implantable, water-based gelatinous (hydrogel) wound dressing intended to act as a protective covering in the management of a variety of partial thickness dermal wounds. Keratin is a structural, filamentous protein that, when hydrated, forms a hydrogel that provides coverage and maintains a moist environment for injured skin, similar to collagen and other extracellular matrix molecules used in existing products. Therefore, KeraStat Gel is expected to behave in an equivalent manner to conventional biopolymer wound dressings. ISO 10993 biocompatibility studies and performance testing, both *in vitro* and *in vivo*, indicated that KeraStat Gel is safe and biocompatible. Additionally, two clinical studies support the assertion that the product is non-sensitizing, non-irritating, and does not produce a humoral response. The current study is designed to evaluate the effectiveness of KeraStat Gel in improving scarring cosmesis when topically applied as a primary dressing to human subjects with partial thickness burns. We hypothesize that use of KeraStat Gel, as compared to the standard of care (SOC), will result in improved cosmesis of the healed wounds.

Objectives

The primary objective of the proposed research is to determine whether the use of KeraStat Gel as the primary dressing for partial thickness burns results in improved cosmesis of the healed wounds.

Secondary objectives include determining whether KeraStat Gel wound dressing results in less painful dressing changes, faster reepithelialization, and reduction in need for excision and grafting.

³ Delavary, B.M., et al., Macrophages in skin injury and repair. *Immunobiology*, 2011. 216(7): p. 753-762.

⁴ Tandara, A.A. and T.A. Mustoe, The role of the epidermis in the control of scarring: evidence for mechanism of action for silicone gel. *Journal of Plastic Reconstructive and Aesthetic Surgery*, 2008. 61(10): p. 1219-1225.

⁵ Mustoe, T.A. and A. Gurjala, The role of the epidermis and the mechanism of action of occlusive dressings in scarring. *Wound Repair and Regeneration*, 2011. 19: p. S16-S21.

⁶ Steinstraesser, L., et al., Pressure Garment Therapy Alone and in Combination with Silicone for the Prevention of Hypertrophic Scarring: Randomized Controlled Trial with Intraindividual Comparison. *Plastic and Reconstructive Surgery*, 2011. 128(4): p. 306E-313E.

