⁷ Bloemen, M.C.T., et al., Prevention and curative management of hypertrophic scar formation. *Burns*, 2009. 35(4): p. 463-475.

Protocol version: 5

Template updated 5 Jul 2021

Methods and Measures

Design

This study is a randomized, controlled, within-subject trial examining the effectiveness of KeraStat Gel, as compared to the institutional SOC, Mepilex Ag, in improving wound cosmesis. Once the Investigator has determined the subject is a candidate for inclusion in the study, the subject will be approached about enrolling in this study. A total of 30 burn subjects presenting to the Burn Centers will be enrolled.

Upon presenting to the hospital, potential study subjects will be assessed for inclusion and approached for consent, as appropriate. Once the subject and/or legal guardian has consented to participate in the study, baseline assessments can be completed. We anticipate that the majority of subjects presenting with burns that qualify for inclusion in the study will have at least one night stay in the hospital; however, this is not criteria for inclusion. KeraStat Gel and Mepilex Ag will each be randomized to application on one of two identified burn sites on the subject, Burn A or Burn B. All subjects will have one burned area dressed with KeraStat Gel and a second area dressed with Mepilex Ag per SOC. The Investigator or study staff will initially apply the dressings per a computer-generated randomization scheme. The burn dressed with KeraStat Gel will have a secondary dressing of petrolatum gauze and telfa. For subjects who have more than two burns, all additional burns will be treated according to the physician's discretion. Subjects will be provided with enough KeraStat Gel and KeraStat Gel-related dressing supplies upon hospital discharge to accommodate prescribed dressing changes until their next visit. The Investigator will instruct subjects on dressing changes as required by institutional SOC guidelines and instructions for use of KeraStat Gel prior to discharge. The need to maintain treatment consistency will be stressed; Burn A and Burn B should always receive their designated dressing.

For the first 4 weeks, subjects will have weekly visits with site staff. On days 7 and 21, this visit will be remote. On days 14, and 28, this visit will be an office visit.

[figure not shown]

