During remote visits, adverse event recording will be recorded by the site. If the subject has agreed to the use of the Engage application on their phone, the subject will also complete a pain assessment for each burned area (Burn A and Burn B). For the Engage application, the subject number will be obtained for registration and completion of the e-diary. The subject will set up a personal identification number (PIN) and provide responses to security questions that will be used if they forget their PIN. The e-diaries will be completed via a web application on the mobile phone that is hosted in a database. As a Software-as-a-Service (SaaS) provider of clinical trial software and services, Clinical Ink acts as an agent on behalf of customers to collect Clinical Study Data. With respect to all Clinical Study Data, the collecting and processing of data are governed by the contractual relationship with each customer consistent with the notice provisions specified by the customer in their relationship with the individuals participating in the clinical study.

If the subject agrees to and is able, the subject will capture photographs of the wounds and upload to the MyChart application. Briefly, the subject will obtain the photograph and navigate to the MyChart application utilizing the web-browser on their phone. The subject should then navigate to the “Messaging” center and click “Ask a Question”. From here, the subject selects “New Medical Question.” The subject should choose their study physician and mark a “Visit Follow-Up Question”. They then can attach an image and click send.

During office visits on days 14 and 28, adverse event recording, incidence of infection, assessment of reepithelialization, photography, and a pain assessment will be completed for each burned area (Burn A and Burn B). A \$45 gas card (one per visit) and KeraStat Gel-related dressing supplies will be given to the subject during these visits, as well.

Partial thickness burns that do not require excision and grafting are expected to be fully closed within 21 days. Thus, after assessment at discharge, subjects will be followed bi-weekly until 4 weeks post-burn to ensure appropriate healing. Then, subjects will be seen at 3 months (± 7 days), 6 months (± 7 days), and 1 year (± 14 days) post-enrollment for site photographs and in order to assess the development of scarring using the Patient and Observer Scar Assessment Scale (POSAS), and TEWL measurements.

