Below is a schematic overview of the study.

Optional at-home questionnaire and photographs at virtual visits on weeks 1 and 3

Wound assessments, questionnaires, photographs, TEWL assessment at 3 months, 6 months, 1 year

Setting

This study will be conducted in the Wake Forest (WF) Burn Center and in the University Medical Center New Orleans (UMC). Subjects may continue treatment as inpatients or as outpatients.

Subjects Selection Criteria

- **Inclusion Criteria**

- Males and females, age 6 years and older
- Written informed consent and assent, if applicable (including parent if subject is a minor)
- Presenting with at least two comparable, discrete, and separate partial thickness thermal burns, as determined by the Investigator, measuring 50-1,000 cm² each
- Study wounds identified are partial thickness depth
- KeraStat Gel and Mepilex Ag can be applied to the randomized study burn wounds as definitive care treatment within 72 hours from time of injury
- Overall total body surface area (TBSA) burned < 20%

- **Exclusion Criteria**

- Pregnant or nursing
- Prisoner
- Presence of inhalation injury, as determined by the Investigator
- Injury requiring formal intravenous fluid resuscitation
- Concomitant non-thermal traumatic injuries
- Chronic medical conditions including, but not limited to, documented > renal impairment (Cr > 2.5 mg/dL), hepatic impairment (Total bilirubin > 2.5 mg/dL), thromboembolic disorders, active infection in study wound areas, uncontrolled diabetes (HbA1C > 7%), HIV infection, history of melanoma or systemic malignancy within the last 10 years
- Receiving corticosteroids, immunosuppressive agents, radiation or chemotherapy, topical growth factors, or any other medication the Investigator feels will affect wound healing
- Not expected to live at least 13 months post-burn
- Previously treated with a skin graft at either of the treatment sites

- Chemical or electrical burn
- Proposed study wounds are full thickness
- Any condition the Investigator determines will compromise subject safety or prevent the subject from completing the study

- **Sample Size**
The study size is 30 subjects, two wounds per subject, 30 wounds per treatment cohort resulting in 60 total wounds.

Because this trial is designed to examine long-term outcomes, no interim analyses or stopping rules are planned.

Interventions and Interactions

Intervention: KeraStat Gel

Agent description

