At baseline, demographic and medical history will be collected, and inclusion/exclusion criteria will be confirmed. If the subject meets these criteria, vital signs will be collected, and the wounds will be randomized to treatment including KeraStat Gel dressings or SOC. Two burns identified by the Investigator will be labeled Burn A and Burn B by study staff and noted on the Case Report Form (CRF). The randomization scheme will be generated in nQuery Advisor 7.0 in advance by the study statistician. An adequate, sequentially numbered, opaque, sealed envelope set will be produced prior to the implementation of the protocol for the site to use. These envelopes will be shipped and maintained at the site with the trial staff member designated by the Investigator or the Investigator themselves to conduct randomization. The staff will choose the first envelope in sequence, record the subject ID and date of the randomization on the outside of the envelope. They will open the envelope and reveal the index card with the treatment assignment for Burn A and Burn B, record again the Subject ID and randomization date on that card, and then upload a photo of the completed card with the Subject's source documentation for the clinic visit. No subject may be randomized early into the study. All envelopes at each site must be used in sequential order. Any alterations to this procedure will be considered a protocol violation. Burns will be examined and photographed. The subject will be asked to complete the Visual Analog Scale (VAS) pain score for each burn site on study. Once each treatment is applied, the subject will once again complete the VAS pain score for each burn site. Thus, two VAS pain scores will be collected for each burn at each treatment application by study staff.

Hospital staff will change dressings until the subject is discharged from the hospital. At discharge, the burns will once again be examined and photographed. The subject will be asked

Protocol version: 5

Template updated 5 Jul 2021

to complete the Visual Analog Scale (VAS) pain score for each burn site on study. Once each treatment is applied, the subject will once again complete the VAS pain score for each burn site. Subjects will be provided with enough KeraStat Gel-related dressings to last 17 days. Subjects will be instructed on dressing changing procedures for both burns per institutional SOC guidelines.

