For the primary objective of the study, improved cosmesis will be analyzed using data from the POSAS, as a total score, and separately for the observer score and then the subject score. Changes from baseline will be examined at 3 months, 6 months and again at 1 year post treatment. TEWL will be considered at 3 months, 6 months, and 1 year. This analysis may also consider the baseline status of the burn including depth, surface area, location of the burn injury and subject baseline characteristics (age, concomitant injury).

Protocol version: 5

Template updated 5 Jul 2021

Secondary objectives include determining whether KeraStat Gel wound dressing results in less painful dressing changes, faster reepithelialization, and reduction in need for excision and grafting. Improvement in pain will be assessed using the scoring from the VAS pain scale at Screening, Days 7, 14, 21 and 28. Box plots of the VAS pain scores will be presented displaying the medians and quartiles in each treatment group over time. A nonparametric test will be used to determine changes in the score across time (Kruskal-Wallis) as well. Reductions in excision and grafting will be analyzed by treatment groups using the same methods as the VAS pain score. Median time to 100% reepithelialization by study treatment group will be conducted, mean times (days) will be analyzed using a Wilcoxon test by treatment groups, as well as a time to event analysis for 90% or higher reepithelialization from baseline.

The incidence of adverse events will be reported and summarized by treatment group. Adverse events will be coded in MedDRA by system organ class and preferred terms (PT).

Human Subjects Protection

Subject Recruitment Methods

Subjects who present at the Burn Center at WF or UMC with qualifying burns as determined by the Investigator will be approached for inclusion in the study by study personnel.

Remuneration

Enrolled study subjects will be provided with one \$45 gas card per visit for office visits on days 14 and 28 and months 3, 6, and 12.

Informed Consent

All subjects must give their informed consent in accordance with the informed consent regulations in Title 21 CFR, Part 50. Each subject over 18 years and subjects under 18 and their legally authorized representative will execute written informed consent (and assent if applicable) before any study procedures are conducted. Study personnel will obtain written informed consent in the clinic.

Confidentiality and Privacy

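### The primary POSAS analysis is a change from baseline, but no baseline POSAS is collected, so the change score cannot be computed for any of the 60 wounds

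*Combined protocol and SAP*

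**What the plan says.** The Analytical Plan assigns POSAS to the primary objective, as a total score and then as separate observer and subject scores. The next sentence gives the form of the analysis: "Changes from baseline will be examined at 3 months, 6 months and again at 1 year post treatment". TEWL follows in a sentence of its own, so the change-from-baseline sentence reads as applying to POSAS.

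The timing of POSAS is stated consistently elsewhere. The Summary says: "At months 3, 6, and 12, subjects and study personnel will complete the Patient Observer Scar Assessment Scale (POSAS". The Design section has subjects seen at 3 months, 6 months and 1 year for photographs and "in order to assess the development of scarring using the Patient and Observer Scar Assessment Scale (POSAS), and TEWL measurements". The Interactions section and the visit lists agree. The only other occasion is an early termination visit.

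The comparison the trial is meant to make is also clear. The Rationale states: "We hypothesize that use of KeraStat Gel, as compared to the standard of care (SOC), will result in improved cosmesis of the healed wounds". The Design section states: "This study is a randomized, controlled, within-subject trial examining the effectiveness of KeraStat Gel, as compared to the institutional SOC, Mepilex Ag". The Analytical Plan does not carry that contrast into the POSAS analysis.

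**The concern.** A change score needs two measurements of the same quantity, and here the first is never taken. The primary analysis cannot be run as written, so whoever analyses the trial will have to improvise. The tempting improvisation is to treat the earliest POSAS, at month 3, as the baseline. That would remove month 3 as a result and subtract from months 6 and 12 whatever treatment difference had already appeared by month 3. A lasting benefit fully reached by month 3 would then read as no benefit. The study is open-label, which is a further reason to settle the form of the primary comparison before anyone looks at results.

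**Working it through.** **1. The denominator.** The Sample Size section gives "two wounds per subject, 30 wounds per treatment cohort resulting in 60 total wounds". With 30 subjects, 30 x 2 = 60, which reproduces the stated total. The protocol gives no power calculation to reproduce.

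**2. Is a baseline POSAS scheduled?** The protocol describes baseline procedures in three places.

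| Place | Content | POSAS |
|---|---|---|
| Interactions, narrative opening "At baseline, demographic and medical history will be collected, and inclusion/exclusion criteria will be confirmed" | history, eligibility, vital signs, randomization, examination, photographs, VAS | none |
| Schedule of Events, Baseline Testing list | 5 items: photographs, vital signs, wound examination, concomitant medications, VAS | none |
| Outcome Measure(s) table, Screening/Day 0 column | 10 marked rows (9 with X, 1 as needed) | none |

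In that table the POSAS row is marked only for the 3-month, 6-month and 1-year visits and for early termination. Discharge and the day 7 to 28 visits carry no POSAS either. Narrative, lists and table agree, so this is not an effect of a table broken in text extraction.

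**3. Count.** With full follow-up, planned POSAS records are 60 x 3 = 180. Baseline records are 0 of 60. Changes from a pre-treatment baseline that can be computed are 0 of 180, at 0 of 3 visits.

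**4. Could something else serve as the baseline?**
- *Month 3.* The plan itself asks for a change at month 3, so month 3 cannot be the reference. Used anyway, it gives at most 60 x 2 = 120 of the 180 changes.
- *Early termination.* The visit list limits POSAS there to months 3-12. The table sets no month limit, and Data and Safety Monitoring asks for the 12-month forms at termination. On any of these readings it is a final assessment.
- *The baseline items in the Analytical Plan* (burn depth, area and location; subject characteristics). These are optional covariates and are not on the POSAS scale.
- *A fixed reference value c for both burns.* None is defined. If one were, (K - c) - (M - c) = K - M, where K and M are the KeraStat Gel and Mepilex Ag scores, so it would cancel in the within-subject contrast.
- *A newly added Day 0 POSAS.* The scale rates a scar. The study dressings must be applicable "as definitive care treatment within 72 hours from time of injury", when there is no scar to rate.

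**5. What a month 3 baseline would do.** Let D3 and D12 be the KeraStat Gel minus Mepilex Ag differences at months 3 and 12, and f = D3/D12. The contrast in change from month 3 is
- at month 3: D3 - D3 = 0;
- at month 12: D12 - D3 = (1 - f) x D12.

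| f (assumed) | Share of D12 kept |
|---|---|
| 0 | 100% |
| 0.25 | 75% |
| 0.50 | 50% |
| 0.75 | 25% |
| 1 | 0% |

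The protocol gives no figure for f. If f exceeded 1, meaning a difference that narrows between months 3 and 12, the contrast would change sign.

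**The case against.** The strongest reply is that this is one wrong phrase and not a broken trial. The sentence naming the POSAS total, observer and subject scores can be carried out in full. The change-from-baseline sentence does not itself mention POSAS. No data are lost, the intended contrast is evident from the Rationale and Design sections, and the Analytical Plan promises a separate SAP, not among the documents reviewed, that could state it. In addition, the protocol nowhere proposes month 3 as a baseline, so the table of retained shares describes a misuse and not the plan, and the planned descriptive summaries and listings would still show the month 3 scores.

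Much of this is fair. The primary data are intact, and the month 3 table only illustrates what improvising could cost. Reading the sentence as POSAS is an inference, but the natural one, given its position directly after POSAS and the separate sentence for TEWL. What the reply does not remove is the contradiction: the only form of analysis stated for the primary outcome requires a measurement that the schedule does not collect. A later SAP could replace that analysis but could not supply the missing score.

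**Conclusion.** The concern holds. As written, the primary change-from-baseline analysis of POSAS can be computed for 0 of 60 wounds and at 0 of 3 visits. This follows from the schedule alone and needs no assumption beyond reading that sentence as applying to POSAS. The defect is a mis-specified primary analysis, not a loss of data: with full follow-up, all 30 within-subject pairs have POSAS scores at each of months 3, 6 and 12, and because treatments are randomized between a subject's two burns, their difference can be interpreted without a baseline. How much a makeshift month 3 baseline would distort the result depends on f, which is unknown; over the assumed range 0 to 1 the month 12 contrast keeps between 100% and 0% of the true difference. Because it affects the primary objective at every visit, it must be corrected.

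**What to change.** In the Analytical Plan, delete the change-from-baseline wording for POSAS. State the primary analysis as the within-subject difference, KeraStat Gel burn minus Mepilex Ag burn, in POSAS total score, analysed by a paired method (for example a paired t-test or a Wilcoxon signed-rank test) and reported with a 95% CI. Say explicitly that month 3 is not to be used as a baseline. The baseline burn and subject characteristics can stay as covariates.

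That alone removes the contradiction. As a separate, related step, name one primary visit (for example month 12) before any data are reviewed, and treat the other visits and the separate observer and subject scores as supportive.

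The cost is one or two sentences, carried into the SAP before database lock. No new data, visits or subjects are needed.
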